11.1 Assessment of Safety

For all participants the NHS GGC risk management procedures will be followed and risk assessments will be carried out prior to study visit. For participants held within clinical teams (example, CAMHS), this will be done in collaboration with the participant's clinical team. For participants who may have no service involvement, NHS GGC care planning and safety

procedures will be followed with GP's as point of contact. Participants will also be told if they disclose any risk to themselves or others, we are obligated to share this with their mental health professional/GP. The core research team (trial manager, PhD student, trial therapists) will receive training on risk assessment and management as the ACADEMIC CAMHS team is embedded with specialist children's services, NHS GGC.

11.2 Definitions of adverse events

Adverse Event (AE) – Any untoward medical occurrence in a subject to whom a trial intervention has been offered, including occurrences which are not necessarily caused by or related to that intervention.

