11.3 Serious Advert Event (SAE)

Serious Adverse Event (SAE): An untoward occurrence that:

- a) Results in death
- b) Is life-threatening*
- c) Required hospitalisation or prolongation of existing hospitalisation**
- d) Results in persistent or significant disability or incapacity
- e) Consists of a congenital anomaly or birth defect
- f) Other considered medically important by investigator

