11.4 Recording and reporting of adverse events

All SAEs will be recorded during the study period to ensure participant's safety and reported to the Principal Investigator (PI). Details of SAEs will be added to the SAE report form stored within the trial site files and followed until resolution. The relationship with the study intervention will be assessed for any unexpected SAEs: if considered related and unexpected these SAEs will be communicated to the PI for review and will be reported to the REC and the sponsor according to standard requirements. The Study Steering Committee will also monitor SAEs to ensure that participant's safety is adequately monitored by those independent to the trial administration.

Any SAE occurring to a research participant will be reported to the main REC (i.e. the REC that gave a favourable opinion of the study) where in the opinion of the Principal Investigator (PI), the event was:

- **“Related”** – that is, it resulted from administration of any of the research procedures, and
- **“Unexpected”** – that is, the type of event is not an expected occurrence.

Reporting to the Sponsor

All Related, Unexpected SAEs (RUSAEs) must be reported to the Pharmacovigilance Office immediately (within 24 hours) using the generic non-CTIMP SAE form which is available from http://www.glasgowctu.org/data/SAE_non-CTIMP.pdf. The SAE form should be completed and signed by appropriately delegated staff. The form should be faxed or e-mailed to the PV Office ([contact]) and a copy placed in the Study Site File. If necessary a verbal report can be given by contacting the PV Office on [name]. This must be followed up as soon as possible with a signed written (or electronic) report.

If all of the required information is not available at the time of initial reporting, the investigator must ensure that any missing information is forwarded to the PV Office as soon as this becomes available. The report should indicate that this information is follow-up information for a previously reported event.

The Sponsor in liaison with the CI will carry out an assessment of expectedness prior to submission of the event to the REC.

Reporting to the Research Ethics Committee (REC)

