The PV office will report all RUSAEs to the ethics committee within 15 days of the PV office becoming aware of the event, via the 'report of serious adverse event form' for non-CTIMPs published on the Health Research Authority web site. <http://www.hra.nhs.uk/documents/2015/02/safety-report-form-non-ctimp.docx>. The form will be completed by the Sponsor and will be signed by the Chief Investigator prior to submission.

The Data Monitoring and Ethics Committee will be notified of all such events whether considered to be related to the trial interventions or not. The co-ordinator of the main REC will acknowledge receipt of safety reports within 30 days.

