17.2 Trial Steering Committee

An independent Study Steering Committee (SSC) will be established and will meet approximately six times during the course of the study, consisting of an independent chair, and three other independent members. The members will be proposed by the CI.

The role of the SSC is to provide overall supervision of the trial and ensure that it is being conducted in accordance with the principles of Good Clinical practice (GCP) and the relevant regulations. The SSC should:

- Agree the trial protocol and any amendments
- Provide advice to the investigators on all aspects of the trial
- Have members who are independent of the investigators, in particular an independent chairperson

[figure not shown]
Decisions about continuation or termination of the trial or substantial amendments to the protocol are usually the responsibility of the SSC.

18 Dissemination

We will rapidly report findings in high profile peer-reviewed journals. We have well-developed dissemination routes to policy-makers through our wider academic team's existing voluntary sector partnerships. Our PPIe groups and YPAGs will be key to this engagement work to ensure that Guidelines are presented in a framework of real world journeys through the service landscape.

The parent/carer members of our PPIe group will be instrumental in disseminating our findings to the wider community of young people with symptoms of Borderline Personality Disorder.

19 Timelines

20 References

- 4 Fok ML-Y, Hayes RD, Chang C-K, Stewart R, Callard FJ, Moran P. Life expectancy at birth and all-cause mortality among people with personality disorder. *Journal of psychosomatic research*. 2012;73(2):104-7.

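### Section 11 needs three corrections: the adverse-event definition omits the SAU-alone arm, relatedness is judged only for unexpected SAEs, and one notification rule contradicts itself and names a committee not set up

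*Combined protocol and SAP*

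**What the plan says.** The safety rules are in section 11 of the combined protocol and SAP.

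- **Adverse event (11.2):** "Any untoward medical occurrence in a subject to whom a trial intervention has been offered", whether or not the intervention caused it.
- **Serious adverse event (11.3):** "Serious Adverse Event (SAE): An untoward occurrence that" meets one of six seriousness criteria. Nothing here depends on arm or on having been offered an intervention.
- **Recording (11.4):** "All SAEs will be recorded during the study period". No recording procedure is given for non-serious events in either arm.
- **Relatedness (11.4):** "The relationship with the study intervention will be assessed for any unexpected SAEs". No list of expected events is given.
- **Ethics reporting (11.4):** "Any SAE occurring to a research participant will be reported to the main REC" if, in the PI's opinion, it was both related and unexpected.
- **Oversight (11.4 and 17.2):** "The Study Steering Committee will also monitor SAEs", and under 17.2 "An independent Study Steering Committee (SSC) will be established", with an independent chair and three other independent members.
- **Further notification (11.4, after the sentence on sending related, unexpected SAEs to the ethics committee):** "The Data Monitoring and Ethics Committee will be notified of all such events whether considered to be related to the trial interventions or not".

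Section 13.2 plans no summary of SAEs, overall or by arm. It leaves the detail of all analyses to a later SAP.

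**The concern.** The comparison is BRIDGE plus SAU against SAU alone, so the SAU arm supplies the background rate of events. Safety rules that do not clearly cover that arm, or that collect its events differently, weaken the only comparison that could separate harm from background. Relatedness matters for a similar reason. Sections 2.2 and 3.1 describe a population at high suicide risk, so the most important serious events may be the ones most readily called expected. Finally, staff need to know which events go to which independent body, and 11.4 does not tell them clearly. A feasibility trial should show that harm collection works in both arms before a definitive trial relies on it.

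**Working it through.** The plan states no figure to reproduce, so the check is mainly a comparison of the rules.

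**1. Who is covered**

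| Rule | Section | Population |
|---|---|---|
| AE definition | 11.2 | Those offered a trial intervention |
| SAE definition | 11.3 | No limit by arm |
| SAE recording | 11.4 | All SAEs |
| SAE reporting to ethics committee | 11.4 | Any research participant |

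Section 12.2 randomises 60 in a 1:1 ratio, so 60 × 1/2 = 30 are in SAU alone. They are not offered BRIDGE, and section 10 says that SAU may amount to no intervention. Read literally, 11.2 omits all 30, while the three SAE rules omit none. The mismatch is real, but it concerns non-serious events, which have no recording procedure in either arm.

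**2. Relatedness**

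In 11.4 an SAE is first sorted as expected or unexpected, and only the unexpected branch has a stated relatedness assessment. Without a list of expected events, the sorting is left to judgement. Followed as written, a serious event that arose from the therapy but was classed as expected is not assessed for relatedness. The section also uses two standards. One refers to the study intervention and the other to any research procedure, and only the second has a clear meaning for an SAU participant.

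**3. The notification sentence**

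The events just named in 11.4 are related, unexpected SAEs. Those are related by definition, so adding that relatedness does not matter contradicts the antecedent. The sentence could mean all SAEs or only the related, unexpected ones. The committee it names appears nowhere else in the supplied text. Section 17 sets up a management group and the Study Steering Committee only.

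**4. Opportunity for events to surface**

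Section 10 gives BRIDGE up to 2 assessment sessions plus up to 16 CAT sessions, 2 + 16 = 18. Both arms share the 12- and 24-week assessments. No method or schedule for asking about SAEs is given.

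As an illustration, assume a true SAE risk of 10% in both arms. The expected count is 30 × 0.10 = 3 per arm. Let *a* be the fraction of SAU events recorded, with recording complete in BRIDGE. The expected recorded counts are 3 and 3*a*, and their ratio is 1/*a*, whatever risk is assumed:

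- *a* = 1: 3 v 3, ratio 1.
- *a* = 0.5: 3 v 1.5, ratio 2.

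Both the risk and *a* are assumptions. The documents give neither.

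**5. The period**

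Sections 5.2 and 5.3 time follow-up from randomisation. Sections 6.2 and 12.2 time it from the end of the intervention, a point SAU alone does not have. The study period in the SAE recording rule is not defined, so the observation window could differ by arm.

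**The case against.** The best defence is that the operative rules concern SAEs and already cover everyone. The AE definition drives no count, because non-serious events are not collected in either arm. That stands. A reader might infer from 11.2 that serious events in SAU would go unrecorded, giving 3 v 0 in the illustration. Sections 11.3 and 11.4 do not support this.

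A reader might also infer that review of events regardless of cause goes only to a committee that does not exist. That fails too, because the Study Steering Committee is set up and monitors SAEs without a limit to related ones. A listing of the other committee on pages missing from the supplied text cannot be excluded.

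On relatedness, ethics reporting requires an event to be both related and unexpected, so screening on expectedness first is sufficient for that purpose. The PI's opinion on both could also be read as covering every SAE. The first argument holds for ethics reporting, but it does not supply the relatedness record needed to describe harms. The second is not what the explicit assessment rule says.

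Unequal collection is softened by safeguards common to both arms. Risk procedures apply to all participants (11.1), and the Suicidal Ideation Scale covers self-harm and attempts at 12 and 24 weeks (Table 1). Nothing, however, links that scale to SAE recording, and it does not capture other kinds of SAE.

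The missing SAE table is weak evidence on its own, since a detailed SAP is still to come. About three events per arm could not settle a question of harm under any definition.

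**Conclusion.** The point holds as three defects in stated rules, not as a demonstrated loss of safety data.

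1. Taken literally, the AE definition omits 30 of 60 participants and does not match the wording of 11.4.
2. Serious events classed as expected escape relatedness assessment, which matters in a population at high suicide risk.
3. The notification sentence contradicts itself and names a committee not constituted in the supplied text, alongside one that is.

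Under-counting in SAU is possible through unequal contact, up to 18 extra sessions in BRIDGE, but its size is unknown. The 3 v 1.5 figure rests on an assumed 10% risk and an assumed halving of recording. These are corrections the sponsor should make. They do not affect the primary outcomes of recruitment and retention.

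**What to change.** - **11.2:** define adverse events for every randomised participant in either arm, over one stated period counted from randomisation. Reconcile 6.2 and 12.2 with 5.2 and 5.3 so that the period is unambiguous, and say whether non-serious events are recorded.
- **11.4, relatedness:** record a relatedness judgement for every SAE, expected or not, against one standard usable in both arms.
- **11.4, notification:** name the Study Steering Committee, or set up the Data Monitoring and Ethics Committee in section 17. State whether it receives all SAEs or only related, unexpected ones.
- **Collection:** ask about SAEs with the same question at the existing 12- and 24-week assessments in both arms. It can go in the section 7.2 booklet.
- **13.2 or the SAP:** report SAEs by arm, as participants and as events.

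The cost is small: a few wording changes, one standard question at visits already planned, a few more relatedness judgements and one table. The Study Steering Committee already has SAE monitoring in its remit, so naming it needs no new body. Setting up a separate committee would cost more.

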11.3 Serious Advert Event (SAE)

Serious Adverse Event (SAE): An untoward occurrence that:

- a) Results in death
- b) Is life-threatening*
- c) Required hospitalisation or prolongation of existing hospitalisation**
- d) Results in persistent or significant disability or incapacity
- e) Consists of a congenital anomaly or birth defect
- f) Other considered medically important by investigator

11.4 Recording and reporting of adverse events

All SAEs will be recorded during the study period to ensure participant's safety and reported to the Principal Investigator (PI). Details of SAEs will be added to the SAE report form stored within the trial site files and followed until resolution. The relationship with the study intervention will be assessed for any unexpected SAEs: if considered related and unexpected these SAEs will be communicated to the PI for review and will be reported to the REC and the sponsor according to standard requirements. The Study Steering Committee will also monitor SAEs to ensure that participant's safety is adequately monitored by those independent to the trial administration.

Any SAE occurring to a research participant will be reported to the main REC (i.e. the REC that gave a favourable opinion of the study) where in the opinion of the Principal Investigator (PI), the event was:

- **“Related”** – that is, it resulted from administration of any of the research procedures, and
- **“Unexpected”** – that is, the type of event is not an expected occurrence.

Reporting to the Sponsor

All Related, Unexpected SAEs (RUSAEs) must be reported to the Pharmacovigilance Office immediately (within 24 hours) using the generic non-CTIMP SAE form which is available from http://www.glasgowctu.org/data/SAE_non-CTIMP.pdf. The SAE form should be completed and signed by appropriately delegated staff. The form should be faxed or e-mailed to the PV Office ([contact]) and a copy placed in the Study Site File. If necessary a verbal report can be given by contacting the PV Office on [name]. This must be followed up as soon as possible with a signed written (or electronic) report.

If all of the required information is not available at the time of initial reporting, the investigator must ensure that any missing information is forwarded to the PV Office as soon as this becomes available. The report should indicate that this information is follow-up information for a previously reported event.

The Sponsor in liaison with the CI will carry out an assessment of expectedness prior to submission of the event to the REC.

Reporting to the Research Ethics Committee (REC)

The PV office will report all RUSAEs to the ethics committee within 15 days of the PV office becoming aware of the event, via the 'report of serious adverse event form' for non-CTIMPs published on the Health Research Authority web site. <http://www.hra.nhs.uk/documents/2015/02/safety-report-form-non-ctimp.docx>. The form will be completed by the Sponsor and will be signed by the Chief Investigator prior to submission.

The Data Monitoring and Ethics Committee will be notified of all such events whether considered to be related to the trial interventions or not. The co-ordinator of the main REC will acknowledge receipt of safety reports within 30 days.

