5.1.2 Intervention

Brief, intensive assessment and integrated formulation (BRIDGE) intervention development has been guided by a) the emerging evidence base for Cognitive Analytic Therapy (CAT) with young people (age 15-25) with BPD in an early intervention service and b) in collaboration with an established Glasgow intervention programme, called Intensive Support and Monitoring Service (ISMS), used in the Glasgow youth justice system. ISMS has the explicit focus of reaching a shared formulation with the young person and the multi-agency system that supports them.

BRIDGE is delivered over 3-6 months and has a three-fold focus:

Firstly, an intensive (post-randomisation) assessment, taking up to two sessions, including BPD symptoms, copresenting difficulties, neurodevelopmental profile, life events history and psychosocial functional impact.

Secondly, up to 16 sessions of Cognitive Analytic Therapy (CAT).

Thirdly, development of a shared formulation with a multi-agency group; further development of the shared formulation with the young person, using CAT principles (Reformulation, Recognition and Revision) and, where clinically applicable, their family and service-providers.

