5.2 Procedure

Our three-month pre-trial set-up phase will establish a detailed system for managing referrals and randomisation and network between the various services from whom we would receive referrals (see section 5.1.1), including any self-referrals/completed online questionnaires. All potential participants will receive a 'Participant Information Leaflet' and a 'Trial Consent Form' prior to Screening 1.

On completion of the Participant Information sheet (online or paper format) and consent form from young people (age 14-24), and from parents and assent from children (age 14-16 who are judged by a healthcare professional as incapable of providing consent), the trial research team (trial manager and research associate) will ensure eligible adolescents and young people are invited to screening 2 with a clinician, prior to study randomisation. Capacity to consent will be confirmed and documented by a healthcare professional at screening 2, prior to randomisation.

Randomisation will be controlled by the Trial Team at the University of Glasgow, who will randomise patients (1:1) to BRIDGE (+SAU) or SAU. The trial manager will generate a randomisation list to ensure data collector blindness. The randomisation list containing the unique study ID and participant name will be stored in a password protected file within the Trial Team's private Microsoft Teams channel (following GDPR guidelines at the university of Glasgow secure server), and access will be restricted only to those members of the research team who will remain unblinded throughout the study. A log of access will be maintained.

All participants consenting to participate will be invited to complete assessments, post randomisation, at baseline, 12 and 24 weeks follow up. A minimum data set of care pathways will be described at baseline and follow-up for all participants, for the purposes of future modelling of health economics impacts, in relation to putative quality of life and functional outcomes measures. Case-study methodology will be used to understand individual contexts, involving qualitative interviews with fourteen young people (seven from BRIDGE intervention and seven from SAU's) and, where possible, their parents and relevant service providers. Topics will include acceptability of the three elements of BRIDGE, perceived mechanisms of change and exploration of requirements for data collection for a future d-RCT, including for future health economic evaluation.

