6.1 Centre and Investigator selection

This is a multi-site trial, with trial office located at the Department of General Practice within the University of Glasgow. The following documents will be in place and copies available in the Trial Master File before recruitment of participants:

- A signed Study Agreement (CI and sponsor signature)
- The approval from the Centre's R&D Department, or organisational approval from non NHS organisations
- Completed Signature List and Roles and Responsibilities document
- Completed contacts list of all site personnel working on the Study
- Consent/assent form and PIS on letter headed paper

The NHSGG&C is included as an identified site for this study as patient notes held by the NHSGG&C will be accessed by the trial team. If remote data collection/therapeutic work is not an option for participants, they will be offered the opportunity to meet at an easily accessible location (e.g. GP surgery or public library). We will follow all local Covid guidance e.g. a phone call will be made to ensure that the participant is feeling well and has no symptoms prior to attending the appointment.

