7.2 Data Collection forms

A user-friendly booklet will be developed by the trial team incorporating relevant demographic and health economic information, as well as the following psychometrics:

Table 1. Baseline and follow-up assessments for the feasibility trial (The BRIDGE project)

Measure*	Baseline	12 wks	24 wks	What measuring?
Questionnaires				
SCID-II PQ-BPD	✓	✓	✓	BPD symptoms (self-reported)
SCID-II DSM-V (BPD module)	✓	✓	✓	BPD criteria (>3 or above out of 9 domains)
KIDSCREEN10	✓	✓	✓	Overall Functioning
Care pathways record and minimum data set	✓			Demographics, pathways to care
Questionnaires				Intensive assessment (BRIDGE)
K-SADS/PL	✓			Assessment of lifetime and present psychopathology
Adverse Childhood Experiences Scale	✓			Adverse childhood experiences
Autism Symptoms adolescents (ASSERT)	✓			Autism assessment
Adult ADHD Self-Report Scale (ASRS)	✓			ADHD symptom checklist
Putative outcome measures of change				Possible mechanisms of change
Borderline symptoms list (BSL-23)	✓	✓	✓	BPD symptom severity
Sheehan's Disability Scale (SDS)	✓	✓	✓	Functioning: work/school, social and family life
Difficulties in Emotional Regulation Scale-SF	✓	✓	✓	Domains of emotional regulation
Patient Health Questionnaire-9	✓	✓	✓	Severity of depression
Quality of life Questionnaire (EQ-5D)	✓	✓	✓	General health related quality of life

ICECAP-A	✓	✓	✓	Wellbeing assessment (Economic Evaluation)
Suicidal Ideation Scale	✓	✓	✓	Suicidal thinking and behaviours (ideation, self-harm, attempts)
Vocational and Educational functioning	✓	✓	✓	School and work (Paid and Unpaid) engagement

* The outcome measures for baseline and follow-up assessments have been selected after consulting the Delphi report from International Committee for Harmonization of Outcome Measures for Personality Disorder (http://www.netscc.ac.uk/hsdr/files/project/SDO_FR_08-1404-083_V01.pdf)

8 Randomisation

Randomisation will be controlled by the Trial Team at the University of Glasgow, who will randomise participants (1:1) to BRIDGE (+SAU) or SAU (see section 10). The trial manager will generate a randomisation list to ensure data collector blindness. The randomisation list will be stored in a password protected file within the Trial Team's private Microsoft Teams channel, and access will be restricted only to those members of the research team who will remain unblinded throughout the study. A log of access will be maintained.

9 Withdrawal & loss to follow-up

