Participants have the right to withdraw consent for participation in any aspect of the BRIDGE trial at any time. The participants care will not be affected at any time by declining to participate or withdrawing from the trial.

A participant may withdraw or be withdrawn from the intervention for the following reasons:

- Withdrawal of consent by participant request
- Any alteration in the participants condition or circumstances which justifies the discontinuation of the intervention in the investigators opinion

If a participant is to be withdrawn, a discussion will take place with the participant – and if necessary with his/her legal representative. The data collected till the point of withdrawal will be retained and this will be clearly documented in participant information sheet and consent form.

The research team will complete a withdrawal form for all participants who consent and subsequently withdraw. This withdrawal form will be retained in the study file. Any queries relating to potential withdrawal of a participant should be forwarded to the Trial Manager.

Upon recruiting participants to the trial, we will gather contact information for them and will explain the plans for future contact. The study does not involve a long period of contact with participants, and therefore we do not expect to lose contact with a high proportion of participants. One of the aims of this study is to determine retention rates.

10 Intervention

Brief, intensive assessment and integrated formulation (BRIDGE) intervention development has been guided by a) the emerging evidence base for Cognitive Analytic Therapy (CAT) with young people (age 15-25) with BPD in an early intervention service and b) in collaboration with an established Glasgow intervention programme, called Intensive Support and Monitoring Service (ISMS), used in the Glasgow youth justice system. ISMS has the explicit focus of reaching a shared formulation with the young person and the multi-agency system that supports them.

BRIDGE is delivered over 3-6 months and has a three-fold focus:

- 1) An intensive (post-randomisation) assessment, taking up to two sessions, including BPD symptoms, co-presenting difficulties, neurodevelopmental profile, life events history and psychosocial functional impact.
- 2) Up to 16 sessions of Cognitive Analytic Therapy (CAT).

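### No prompt, source or window is set for recording SAEs, and BRIDGE has up to 16 to 18 more trial contacts than SAU alone, so any by-arm view of SAEs would be open to differential ascertainment

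*Combined protocol and SAP*

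**What the plan says.** - **Recording rule.** Section 11.4: "All SAEs will be recorded during the study period to ensure participant's safety and reported to the Principal Investigator (PI". Related and unexpected SAEs go on to the sponsor and the ethics committee, and the Study Steering Committee (SSC) monitors SAEs. The section does not say how or when participants are asked, which records are searched, or when the period starts and ends.
- **Schedule.** Table 1 (Section 7.2) has no adverse event or SAE row.
- **Contacts in BRIDGE only.** Section 10 lists "An intensive (post-randomisation) assessment, taking up to two sessions" and "Up to 16 sessions of Cognitive Analytic Therapy (CAT". Section 11.1 counts the trial therapists as core research team.
- **Contacts in both arms.** Section 5.2: "All participants consenting to participate will be invited to complete assessments, post randomisation, at baseline, 12 and 24 weeks follow up". Sections 5.1.3 and 10 accept that SAU may amount to no service at all.
- **Channels open to both arms.** Section 11.1: "risk assessments will be carried out prior to study visit". Table 1 includes a Suicidal Ideation Scale covering "Suicidal thinking and behaviours (ideation, self-harm, attempts" at baseline, 12 and 24 weeks. Sections 5.5 and 13.2 collect service use for the economic analysis. Section 6.1 says "patient notes held by the NHSGG&C will be accessed by the trial team". None of these is tied to the SAE form.
- **Analysis.** Section 13.2 plans no between-arm SAE comparison.

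**The concern.** An SAE enters the record only if someone in the trial hears of it. In BRIDGE, a therapist who belongs to the research team may see the participant at up to 18 sessions. In SAU alone, the trial's scheduled contact after baseline is at 12 and 24 weeks, and some participants have no clinician who could pass on news of an admission. With no common question or source, the chance that an event is recorded can depend on the arm.

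Two uses of the SAE record are exposed. The SSC monitors SAEs, and the third closure criterion in Section 15 allows it to end the trial when new information makes randomising to one of the arms inappropriate. That is an arm-specific judgement to which SAE counts are an obvious input. The final report may also show SAEs by arm. In either place an excess in BRIDGE could be a detection artefact, and a real excess could be dismissed as one. Section 4.3 also asks whether data systems can be set up for a definitive trial; without a defined SAE method, harms collection goes untested.

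**Working it through.** The plan states no SAE rate or contact total, so there is no figure of its own to reproduce.

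**1. Contact counts (Sections 5.2 and 10).**
- BRIDGE-only sessions, at most: 2 + 16 = 18.
- Shared follow-ups after baseline: 2 (12 and 24 weeks).
- Ceiling: 18 + 2 = 20 contacts in BRIDGE against 2 in SAU alone.
- Sections 4.3 and 5.3 list post-randomisation assessments without naming an arm, while Table 1 labels that block as the BRIDGE intensive assessment. If SAU also receives them, the excess falls towards 18 − 2 = 16.

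**2. Effect of unequal capture.** Let the true SAE risk p be equal in both arms and d be the probability that an affected participant's event is recorded. The recorded rate is p × d, so the apparent ratio is d(BRIDGE) / d(SAU), whatever p is. With 60 randomised 1:1 (30 per arm), a 10% risk is 3 affected participants per arm and a 20% risk is 6. All values of p and d are assumptions.

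| d BRIDGE | d SAU | Apparent ratio | Recorded at p = 10% | Recorded at p = 20% |
|---|---|---|---|---|
| 0.95 | 0.90 | 1.06 | 2.85 v 2.70 | 5.7 v 5.4 |
| 0.95 | 0.80 | 1.19 | 2.85 v 2.40 | 5.7 v 4.8 |
| 0.95 | 0.70 | 1.36 | 2.85 v 2.10 | 5.7 v 4.2 |
| 0.95 | 0.50 | 1.90 | 2.85 v 1.50 | 5.7 v 3.0 |

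**3. A contact model as a cross-check.** If each contact brings out an event with probability q, then d = 1 − (1 − q)^k, with k = 20 in BRIDGE and k = 2 in SAU.
- q = 0.9: 1.00 / 0.99 = 1.01
- q = 0.5: 1.00 / 0.75 = 1.33
- q = 0.3: 0.999 / 0.51 = 1.96
- q = 0.1: 0.878 / 0.19 = 4.62

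This model uses the ceiling on contacts, treats them as independent, treats every contact as following the event, and ignores notes and other channels. It shows direction and sensitivity, not a likely size.

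**4. Precision.** The 95% half-width for a risk difference with 30 per arm is 1.96 × √(2p(1 − p)/30): about 15 points at p = 10% and 20 points at p = 20%. The largest artefact in the table is (5.7 − 3.0)/30 = 9 points.

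**5. After the change.** If both arms are asked the same questions at the same two visits and only those events are compared, k = 2 in each arm. The apparent ratio is then 1.00 at any q, given equal true risk and equal retention.

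**The case against.** The strongest reply is that no harm comparison is planned, so there is nothing to bias. That is right about Section 13.2. A reader might infer that the trial will publish a biased between-arm estimate of harm, or will carry SAE rates into the definitive trial. The documents support neither: they carry forward recruitment and retention parameters and standard deviations. What stands is the SSC's monitoring role and the arm-specific closure criterion.

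The second reply is that channels open to both arms already exist. The risk procedures in Section 11.1 apply to all participants, with the GP as contact where no service is involved; the suicidality scale, service-use data and NHS notes could also reveal events. It would therefore go too far to say that SAU admissions will be missed, or that SAU participants lost to follow-up yield no SAE information. But nothing routes these channels into the SAE record. The scale does not cover other admissions or disability. Sections 5.2 and 5.5 promise care-pathway data at follow-up, yet Table 1 ticks that record at baseline only.

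Third, 20 against 2 is a ceiling, not expected exposure. Sessions are capped rather than fixed, the assessments may be shared, and seven SAU participants are also interviewed. Nor do the documents show that SAU follow-up is mostly self-completed: telephone interview is offered, and the SCID-II module is repeated at both follow-ups.

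Fourth, it is tempting to say that SAEs are captured passively. Section 11.4 is silent on method, so that is an inference.

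Finally, with 30 per arm any SAE comparison is imprecise, and the assumed artefact is smaller than the half-width. That limits formal inference, but it does not protect a committee reading small counts by arm.

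**Conclusion.** The point holds as a gap in how SAEs are found. The protocol sets no prompt, source or window common to both arms, and its contact schedule gives BRIDGE up to 16 to 18 more occasions on which an SAE can surface. Any by-arm view would be open to differential ascertainment, most likely raising the BRIDGE count.

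The size cannot be derived from the documents. Under equal true risk, the apparent ratio runs from about 1.0 if the shared contacts or notes capture nearly all events to about 1.9 at an assumed 95% capture in BRIDGE against 50% in SAU. It could be negligible in practice, but the plan contains nothing to ensure that. The change is worth making because it is cheap and uses visits and records already in the plan.

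**What to change.** - Add an SAE row to Table 1 at 12 and 24 weeks, with the same short questions in both arms (admissions, life-threatening events and the other criteria in Section 11.3), asked by the blinded assessor.
- In Section 11.4, add a check of the NHS GG&C notes the team already plans to access, for every randomised participant, including those lost to follow-up, where consent allows.
- State one common window starting at randomisation. Reconcile the timing of follow-up first: Sections 5.2 and 5.3 count it from randomisation, Sections 6.2 and 12.2 from the intervention.
- Tabulate SAEs by arm from this common source, and list separately any events known only from therapy sessions.
- Leave immediate SAE reporting unchanged.

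The cost is about one extra page of questions, some 60 notes checks, and a check that the consent wording covers them, since Section 6.1 does not say what the notes access is for. Notes held outside NHS GG&C would not be covered.
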